7.1.4 Post-Surgery until Hospital Discharge

Prior to discharge, the following blood samples must be drawn and data will be recorded:

- Post-operative blood samples will be taken for Full Blood Count (FBC) with Differential and Coagulation parameters (PT, aPTT, INR). The last set of blood samples taken prior to discharge will be recorded:
- Physical examination as per institutions normal procedure;
- Concomitant medications;
- Details of hospital stay including: date of hospital discharge; overall stay in days (admission to discharge); ventilator time (if applicable);
- Incidence of adverse events; and
- Incidence of potential bleeding-related complications, including thrombotic events.

7.1.5 30-day Follow-Up Visit (±14 days)

The following information will be recorded during and in person visit or phone call, approximately 30 days following surgery:

- Changes in concomitant medications, including use of any blood products following hospital discharge;
- Incidence of adverse events; and
- Incidence of potential bleeding-related complications, including thrombotic events.

7.2 Procedures for Handling Biological Samples

7.2.1 Laboratory Tests

All laboratory investigations for FBC and Coagulation parameters will be performed at the local hospital laboratory. The volume of blood to be taken will be determined according to the standard practices of each hospital. The normal reference ranges and laboratory accreditation certificates must be provided to ETHICON. Local labs will be performing the tests in a blinded fashion as the local labs will not be aware of the randomized treatment.

EudraCT Number: 2013-003401-26 Page 22 of 35

Amendment 4: 08 January 2018

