If additional soft tissue or parenchymal organ bleeding sites are identified, the surgeon may treat with the same treatment product according to the subject's randomization assignment, if clinically appropriate or their preferred standard of care. Haemostatic assessment of these additional bleeding sites will not be recorded.

TEST PRODUCT:

EVICEL® Fibrin Sealant (Human)

STUDY POPULATION:

Paediatric subjects, undergoing non-emergent abdominal, retroperitoneal, pelvic or thoracic (non-cardiac) surgery procedures, wherein an appropriate TBS is identified. Paediatric subjects for this study are defined as:

- Neonates (birth to 30 days) with pre-term neonates born ≤37 weeks gestation included within this group;
- Infants and toddlers (31 days to <24 months);
- Children (2 to 11 years); and
- Adolescent (12 to 18 years).

CONFIDENTIAL

Protocol: 400-12-006 Amendment 4: 08 January 2018

PRIMARY ENDPOINT:	Absolute time to haemostasis, defined as absolute time when there is no detectable bleeding at the Target Bleeding Site (TBS).
SECONDARY ENDPOINTS:	 Haemostasis at 4, 7 and 10 minutes following randomization; Incidence of treatment failures (defined as haemostasis not achieved within 10 minutes or bleeding at the TBS during the ten-minute observational period that requires further haemostatic measures other than re-application of the assigned haemostatic adjunct); Incidence of adverse events (including thrombotic events and events associated with TBS re-bleeding); Proportion of subjects with no- rebleeding; and Haemoglobin, Haematocrit, Platelets, Volume of blood loss, Volume of blood and blood products transfusions.
SAFETY:	Adverse events will be collected from time of randomization, throughout the follow-up period of 30 (± 14) days. Intra-operative bleeding at the TBS after 10 minutes will be an adverse event.

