4.1.1 Inclusion Criteria

Pre-operative:

- 1. Paediatric subjects birth to <18 years of age, requiring non-emergent laparoscopic or open abdominal, retroperitoneal, pelvic or thoracic (non-cardiac) surgical procedures.
- 2. The subject and/or subject's parent or legal guardian must be willing to give permission for the subject to participate in the trial, and provide written informed consent for the subject. If possible, assent must be obtained from paediatric subjects who possess the intellectual and emotional ability to comprehend the concepts involved in the trial If the paediatric subject is not able to provide assent (due to age, maturity and/or inability to intellectually and/or emotionally comprehend the trial), the parent/legal guardian's written informed consent for the subject will be acceptable for the subject to be included in the study.

Intra-operative

3. Presence of an appropriate mild or moderate bleeding soft tissue or parenchymal organ Target Bleeding Site identified intra-operatively by the surgeon;

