8.1 Sample Size Determination

No formal sample size determination is required for this study, however a total of at least 40 subjects, 20 in each group, is a sufficient sample size to achieve the study objectives.

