8.4.2 Methods of Analysis

Adverse events will be summarised descriptively by the treatment received, using Medical Dictionary for Regulatory Activities (MedDRA) terminology. Coagulation parameters (baseline and post-surgery samples) will use SI units.

Laboratory values (including coagulation parameters) will be reported in International System (SI) units. Values and changes from baseline will be listed and summarised. Clinically significant changes will be reported as part of the AE summary.

.

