3.1.5	Summary of during/post treatment surgical procedure related (possibly, definitely) adverse events by subject and coded terms – Safety analysis set	Includes adverse events for which the answer for CRF item "Relationship to surgical procedure" is "Possibly related" or "Related".	AM
3.1.6	Summary of during/post treatment study treatment related (possibly, definitely) adverse events by patient and coded terms – Safety analysis set	Includes adverse events for which the answer for CRF item "Relationship to study treatment" is "Possibly related" or "Related".	AM
3.2	Laboratory data	Reported in SI units	
3.2.1	Laboratory data: Full Blood Count - Safety analysis set	At screening, at baseline, and post-surgery to hospital discharge - within 72 hours prior to discharge)	L
3.2.2	Laboratory data: White Blood Cell Differential - Safety analysis set	At screening, at baseline, and post-surgery to hospital discharge - within 72 hours prior to discharge)	L
3.2.3	Laboratory data: Coagulation Parameters - Safety analysis set	At screening, at baseline, and post-surgery to hospital discharge - within 72 hours prior to discharge)	L
3.3	Other safety data		
3.3	Safety/secondary endpoints  – Safety analysis set	Incidence of treatment failures (defined as haemostasis not achieved within 10 minutes or bleeding at the TBS during the ten-minute observational period that requires further hemostatic measures, other than re-application of the assigned hemostatic adjunct), incidence of subjects with thrombotic events, incidence of subjects with events associated with TBS re-bleeding, proportion of subjects with no re-bleeding (all d), estimated intra-operative blood loss (mL) (c), and volume of blood and blood products transfusions (red blood cells, fresh frozen plasma, platelets, and cryoprecipitates), intra-operatively, prior to hospital discharge, and after discharge (all c)	G2

Note: '-' indicates a new line in the title.

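### Laboratory ranges are collected across local laboratories and all paediatric ages, but the SAP text specifies no range-based summary and drops the change-from-baseline summary that the protocol promises

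*Protocol*

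**What the plan says.** **Where the tests are done.** Protocol 7.2.1: "All laboratory investigations for FBC and Coagulation parameters will be performed at the local hospital laboratory". The same section adds: "The normal reference ranges and laboratory accreditation certificates must be provided to ETHICON". It does not say that these ranges are split by age.

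**Who is tested.** Protocol 4.1.1 admits "Paediatric subjects birth to <18 years of age". The youngest group in the synopsis is "Neonates (birth to 30 days) with pre-term neonates born ≤37 weeks gestation included within this group".

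**What is summarised.** Protocol 8.4.2: "Laboratory values (including coagulation parameters) will be reported in International System (SI) units". It then says that values and their changes from baseline will be both listed and summarised, and that clinically significant changes go into the adverse event summary. SAP 9.1 names haemoglobin, haematocrit and platelets among the safety/secondary endpoints. SAP 10.2.2 plans three laboratory tables for the Safety set: 14.3.2.1 ("Laboratory data: Full Blood Count - Safety analysis set"), 14.3.2.2 (white cell differential) and 14.3.2.3 ("Laboratory data: Coagulation Parameters - Safety analysis set"). Their notes give only the visits, under a group note on SI units. SAP 10.2 sets the general layout as treatment group and, where suitable, visit, with counts, mean, SD, minimum, median and maximum unless something else is stated.

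**What is not specified.** The SAP text mentions no reference range, out-of-range flag, low/normal/high class or shift table. Age groups are specified only for the primary endpoint (SAP 8.2). SAP 9.4 says that values and changes from baseline will go into listings and will not be summarised. SAP section 4 reports no change to the planned analysis.

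**The concern.** A haemoglobin or clotting time has meaning only against what is normal for that child's age in that laboratory. SI units align the scale of measurement but do not align normality. When all ages and laboratories in an arm share one mean, SD, minimum and maximum, the spread mixes treatment-related change with differences in age and assay, and no row says how many children were in range before surgery and out of range after it.

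Two planned elements could have dealt with this. The ranges would allow each value to be classified. Within-child change would remove any age or laboratory difference that is stable and additive. The SAP text gives the first no role, and it takes the second out of the tables. What is at stake is how readable the laboratory safety data are, including three named secondary endpoints. The primary endpoint is not affected.

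**Working it through.** There is no figure in the plan to reproduce: no laboratory values are given, and the sample size has no formal calculation. The check is therefore a comparison of passages, followed by an illustration on stated assumptions.

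**1. Change from baseline.** Protocol 8.4.2 has values and changes listed and summarised. SAP 9.4 has them listed only. The SAP sentence follows one about adverse events in SI units. Units have no meaning for adverse events, so it is best read as a shortened form of the protocol's laboratory paragraph. On that reading it contradicts the protocol. Taken literally, it also contradicts SAP 9.1 and Tables 14.3.2.1 to 14.3.2.3, which do summarise laboratory values. SAP section 4 records none of this.

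**2. Which value is baseline.** Protocol 7.1.1 and 7.1.2 collect only the pre-operative result closest to surgery. SAP 9.1, 9.2 and the three tables show screening and baseline separately. A child's single pre-operative value may fall under either visit, so neither pre-operative column need contain the whole arm, and comparing columns is not a clean before/after comparison.

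**3. What pooled statistics can miss.** Inputs: 20 per arm (protocol 8.1: "a total of at least 40 subjects, 20 in each group, is a sufficient sample size") and the four age bands of SAP 8.2. Assumptions: 5 children per band; normal values with within-band SD 1; adjacent band means d apart, with d from 0 to 2. One child, equally likely to be in any band, lies 3 SD below the mean of its own band.

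- Expected shift in the arm mean: 3/20 = 0.15 SD.
- Number the bands 0 to 3 upward by mean. If the child is in band k, the chance that at least one other child lies lower is 1 − Π_j [1 − Φ((k − j)d − 3)]^n_j, with n_j = 4 in the child's own band and 5 in the others.
- At d = 1 this gives 0.006, 0.114, 0.626 and 0.988 for k = 0, 1, 2, 3. The average is 1.734/4 = 0.43.
- The same average at d = 0, 0.5 and 2 is 0.03, 0.14 and 0.65.

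So a child clearly low for age barely moves the mean. Even the minimum belongs to another child in 3%, 14%, 43% or 65% of cases at d = 0, 0.5, 1 and 2.

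**4. What a count would show.** Exact (Clopper-Pearson) 95% intervals for the proportion newly out of range in an arm of 20:

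- 0/20: 0 to 16.8% (upper limit 1 − 0.025^(1/20))
- 1/20: 0.1% to 24.9%
- 2/20: 1.2% to 31.7%

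The chance of at least one such child among 20 is 1 − (1 − p)^20. For assumed true rates p of 5%, 10% and 15% this is 64%, 88% and 96%. The counts would be imprecise but interpretable.

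**The case against.** **The shell has not been seen.** Tables 14.3.2.1 to 14.3.2.3 use shell L, while most other continuous summaries use the generic G2. Shell L is in the Appendix 1 attachment, and the default statistics in SAP 10.2 apply only unless otherwise stated. It may already contain range flags. This stands, and it limits the point to the SAP text. A reader might infer that the ranges are never used, or that the tables cannot show abnormality; the available documents do not establish either.

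**Other routes exist.** Listings 16.2.7.2.1 to 16.2.7.2.3 show laboratory results by subject, SAP 10.3 lists all non-administrative database fields, and about 40 children is a readable number. Clinically significant changes become adverse events (protocol 8.4.1 and 8.4.2). Table 14.2.3 also counts clinically significant changes since baseline, without saying that these are laboratory changes. So it would be wrong to infer that an abnormal child is lost. What remains is that listings give no count by arm and show a range only if it is in the database, and that the adverse event route depends on a judgement for which neither document gives a criterion.

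**The study is descriptive.** SAP 9.4 plans no inferential safety analysis. A reader might argue that pooling ages and laboratories makes the between-arm difference in raw means too imprecise. The plan specifies no such comparison, and adding a shift table would leave that precision unchanged, so the point does not rest on it. A shift table is itself descriptive.

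**Counts would mix causes.** The post-operative sample is the last before discharge (protocol 7.1.4), after surgery and any transfusion. This is true: the counts should be read between randomised arms and not attributed to the product.

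**Conclusion.** The point holds as a minor one. In the text as written, laboratory tables are raw-value summaries by arm and visit, the ranges that the protocol requires have no stated analytical use, and the SAP withdraws a change-from-baseline summary that the protocol promises. No per-arm count of children moving out of range is specified. The contradiction over change from baseline, and the split of the pre-operative value between two visits, follow directly from the documents.

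The size is not known, because the documents contain no laboratory data. The 0.15 SD shift and the 3% to 65% rest on assumed normal values, equal age bands and gaps of 0 to 2 SD. They show that pooled statistics can miss a child who is abnormal for age; they do not show that this will happen here. The missing range-based summary is established for the SAP text only. If shell L already carries flags or shifts, that part reduces to stating so in the text.

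**What to change.** In SAP 9.2 and 9.4 and Tables 14.3.2.1 to 14.3.2.3:

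- Keep the raw SI rows.
- Add, per arm, a low/normal/high shift table from the pre-operative value closest to surgery to the post-surgery value, using each laboratory's range appropriate to the child's age. Define that pre-operative value as baseline.
- Reconcile SAP 9.4 with protocol 8.4.2 by restoring the summary of within-child change from baseline, and remove the conflict with the SAP's own laboratory tables.
- Flag out-of-range values in Listings 16.2.7.2.1 to 16.2.7.2.3.
- If shell L already does part of this, say so in the SAP text.

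The cost is entering the ranges, three extra table panels, and a request to any laboratory that has not supplied paediatric bands. The last item may be needed because the protocol does not ask for age-specific ranges. No extra samples or visits are needed.

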7.3 Premature Withdrawal of Subjects for the Study

All randomized subjects should be encouraged to remain in the study until they have completed the 30-day follow-up visit. Subjects and/or their parent or legal guardian may discontinue participation in the study at any time and for any reason. However, if the subject decides to discontinue participation in the study, the reason must be documented when possible. Reasons for early withdrawal include, but are not limited to:

- Consent withdrawn by the subject and/or parent or legal guardian;
- Subject refusal to complete study visits and/or procedures;
- Lost to follow-up: a recorded delivery letter will be sent to the subject at their last known address, after a minimum of three attempts to reach the subject by telephone have failed. If communication via certified letter is unsuccessful, the subject will be considered lost to follow-up.

Subjects who are randomized and discontinue from the study prematurely will not be replaced.

8 STATISTICAL METHODS

The Data Management and Biostatistics groups of Clinical Development, at Johnson & Johnson Global Surgery Group will be responsible for the overall analysis of data from this protocol. The detailed Statistical Analysis Plan (SAP) will be based on and will supplement the statistical design and analysis described in this section.

8.1 Sample Size Determination

No formal sample size determination is required for this study, however a total of at least 40 subjects, 20 in each group, is a sufficient sample size to achieve the study objectives.

8.2 Data Analysis

The categorical data will be summarised descriptively by frequencies along with associated percentages for each group. The continuous variables will be summarised descriptively by number of subjects, mean, standard deviation, minimum, and maximum for each group. If applicable, a 5% significance level will be used for any statistical tests. Two-sided 95% confidence intervals will be quoted. Two-sided 95% confidence intervals (CIs) for median absolute time to hemostasis will be reported separately for EVICEL® and SURGICEL® groups. For the success/failure data (4, 7 and 10 minute hemostasis endpoints), the 95% CI will be quoted for P_F , P_C and for ratio P_F / P_C , where P_F is the proportion of success in EVICEL® subjects and P_C is the proportion of success in SURGICEL® control subjects. The lower limits of these 95% CI will be utilised for statistical inferences.

8.2.1 Analysis Sets

There will be three analysis sets defined:

- Full analysis set (FAS or intent-to treat) consists of all randomized subjects.
- Per-protocol analysis set (or evaluable) consists of all FAS subjects who have no major protocol violations.
- Safety analysis set will consist of all subjects who received treatment.

If any patients are mis-randomized (randomized to one treatment, but received the other) the FAS will summarise data 'as randomized', and the safety set will summarise 'as treated'.

EudraCT Number: 2013-003401-26 Page 23 of 35

Amendment 4: 08 January 2018

If more than 2 patients are mis-randomized then the data will be summarised 'as treated', within a separate analysis set. Patients who are mis-randomized will be considered major protocol violations.

The primary endpoint analysis will be based on the Full Analysis Set (FAS).

Major protocol violations are violations that have an impact on the primary endpoint. These will be determined prior to database lock.

8.3 Effectiveness

8.3.1 Effectiveness Variables

The following primary endpoint will be analysed using the FAS and Per-protocol Sets:

Absolute time to haemostasis (elapsed from randomization);

The following secondary endpoints will be analysed using the FAS only:

- Haemostasis at the TBS at 4, 7 and 10 minutes following randomization; and
- Incidence of treatment failures (defined as haemostasis not achieved within 10 minutes or bleeding requiring treatment other than re-application of the assigned haemostatic adjunct within 10 minutes).

8.3.2 Methods of Analysis

Descriptive statistical analysis will be conducted overall and by treatment. Primary endpoint data will also be descriptively summarised into Neonates (birth to 30 days), Infants and toddlers (31 days to <24 months), Children (2 to 11 years) and Adolescent (12 to <18 years). Two-sided 95% confidence intervals (CIs) for median absolute time to hemostasis will be reported separately for EVICEL® and control groups. For the success/failure data (4, 7 and 10 minute hemostasis endpoints), the two-sided 95% CI will be quoted for P_F , P_C and for ratio P_F / P_C , where P_F is the proportion of success in EVICEL® subjects and P_C is the proportion of success in SURGICEL® control subjects. The lower limits of these 95% CI will be utilised for statistical inferences.

8.4 Safety

8.4.1 Safety Variables / Criteria

The following will be summarised using the Safety Set:

- Incidence of treatment failures (defined as haemostasis not achieved within 10 minutes or bleeding at the TBS during the ten-minute observational period that requires further haemostatic measures other than re-application of the assigned haemostatic adjunct);
- Incidence of adverse events (including thrombotic events and events associated with TBS rebleeding).
- Proportion of subjects with no rebleeding;
- Laboratory and Blood Loss/Transfusion data will be summarised; and
- Clinically significant events will be recorded as AEs (Haemoglobin, Haematocrit, Platelets, Volume of blood loss; Volume of blood and blood products transfusion).

EudraCT Number: 2013-003401-26 Page 24 of 35

Amendment 4: 08 January 2018

8.4.2 Methods of Analysis

Adverse events will be summarised descriptively by the treatment received, using Medical Dictionary for Regulatory Activities (MedDRA) terminology. Coagulation parameters (baseline and post-surgery samples) will use SI units.

Laboratory values (including coagulation parameters) will be reported in International System (SI) units. Values and changes from baseline will be listed and summarised. Clinically significant changes will be reported as part of the AE summary.

.

8.5 Interim Analyses

None.

8.6 Handling of Missing Data

It is not anticipated that there will be any data missing for treated subjects for the primary endpoint, but if there is, missing data will not be imputed for the primary analysis.

Analyses of secondary endpoints will consider missing data as failures.

9 SAFETY DEFINITIONS

9.1 Adverse event

An adverse event means any untoward medical occurrence associated with the use of a drug in humans, whether or not considered drug related. An adverse event (also referred to as an adverse experience) can be any unfavorable and unintended sign, symptom, or disease temporally associated with the use of a drug, without any judgment about causality. Since post operative pain is an expected outcome of this type of surgery, for purposes of this study, only exacerbations of expected post operative pain based on the Investigator's judgment should be reported as an AE.

The Investigator may also need to consider whether an adverse event is attributable to the application device, based on any of the following:

- Resulting from insufficiencies or inadequacies in the IFU;
- In the actual use of the application device or tips or regulator; or
- The result of user error.

9.2.1 Suspected adverse reaction

A suspected adverse reaction means any adverse event for which there is a reasonable possibility that the drug caused the adverse event. Reasonable possibility means there is evidence to suggest a causal relationship between the drug and the adverse event. A suspected adverse reaction implies a lesser degree of certainty about causality than adverse reaction.

